### **11.3 Objection by minors or incapacitated subjects**

See paragraph 11.2

### **11.4 Benefits and risks assessment, group relatedness**

There are no relevant benefits or risks associated with wearing of the wristband to record PPG data.

### **11.5 Compensation for injury**

The sponsor/investigator has a liability insurance which is in accordance with article 7 of the WMO. The sponsor (also) has an insurance which is in accordance with the legal requirements in the Netherlands (Article 7 WMO). This insurance provides cover for damage to research subjects through injury or death caused by the study.

The insurance applies to the damage that becomes apparent during the study or within 4 years after the end of the study.

**11.6 Incentives**

Not applicable.

## **12. ADMINISTRATIVE ASPECTS, MONITORING AND PUBLICATION**

### **12.1 Handling and storage of data and documents**

The cloud-based electronic data capture (EDC) platform CASTOR EDC will be used to capture pseudonymised patient data. This enables high quality storage and reusability of data. Data entry from the electronic patient record into the EDC system will be performed at the participating study site. The data generated in the studies, including (raw) ECG, PPG and hemodynamic data will be encoded, not based on patient initials and date of birth. The subject identification log will be filed at the participating centre. Processing of personal data will comply to the rules of the General Data Protection Regulation (GDPR). PPG and the other sensor data recorded with the CardioWatch will be collected and stored in a certified cloud-system. Details can be found in the Attachment (Cloud Data Management Description CardioWatch 287). In short, the CardioWatch 287 Cloud system is composed of Web servers running on the cloud (hosted by AWS servers located in Frankfurt, Germany) that collect, store and exchange data with authorized medical partners. The collected raw PPG data will be used for algorithm development and is accessible for the investigators. AWS partner is certified ISO 270001 for IT Security Systems. The Corsano cloud is fully GDPR compliant. Technical details and certificates can be found in the Attachment (Cloud Data Management Description CardioWatch 287).

### **12.2 Monitoring and Quality Assurance**

Independent monitoring will take place for quality assurance. It will be arranged by the Radboudumc and performed at least once a year. Further details can be found in the monitoring plan.

### **12.3 Amendments**

Amendments are changes made to the research after a favourable opinion by the accredited METC has been given. All amendments will be notified to the METC that gave a favourable opinion.

### **12.4 Annual progress report**

The sponsor/investigator will submit a summary of the progress of the trial to the accredited METC once a year. Information will be provided on the date of inclusion of the

first subject, numbers of subjects included and numbers of subjects that have completed the trial, serious adverse events/ serious adverse reactions, other problems, and amendments.

### **12.5 Temporary halt and (prematurely) end of study report**

The investigator/sponsor will notify the accredited METC of the end of the study within a period of 8 weeks. The end of the study is defined as the last patient's last visit.

The sponsor will notify the METC immediately of a temporary halt of the study, including the reason of such an action.

In case the study is ended prematurely, the sponsor will notify the accredited METC within 15 days, including the reasons for the premature termination.

Within one year after the end of the study, the investigator/sponsor will submit a final study report with the results of the study, including any publications/abstracts of the study, to the accredited METC.

### **12.6 Public disclosure and publication policy**

Study results will be published open access according to the arrangements made and described in the clinical trial agreement.

## 13. STRUCTURED RISK ANALYSIS

### 13.1 Potential issues of concern

The study concerns additional diagnostic investigation in the form of collection of PPG data recorded on the skin with a wristband. This does not convey additional risk for the patient. The short-lasting circulatory arrest inductions are part of routine practice during the described procedures and not part of the study protocol. Also for the collection of additional parameters including but not limited to invasive blood pressure measurements, routinely recorded data is used. Monitoring with PPG does not replace any other monitoring tool during the study.

Only for ICD/VT ablation patients, we will ask additional consent to insert an arterial line in the radial artery to measure blood pressure invasively during the procedure as this is not routine practice. In case consent is not given, patients can participate without arterial line insertion. Complications following radial artery cannulation include permanent ischemic damage (0.09%), temporary occlusion (20%), sepsis (0.13%), local infection (0.72%), pseudoaneurysm (0.09%), hematoma (14.4%), bleeding 0.53%. Generally temporary occlusion of the radial artery has no serious sequelae. Permanent occlusion appears to be rare (0.09%) (14). In the majority of studies on which these incidences are based, the arterial line was inserted for longer term invasive monitoring (e.g. during intensive care unit stay). It is expected that complication rates will be lower with planned insertion of an arterial line under optimal circumstances and only for monitoring during the procedure. The product used for PPG recording is a comfortable wristband (CardioWatch 287 - Corsano Health B.V.) intended for continuous collection of physiological data in home and healthcare settings. Recorded data is saved in a certified cloud-based data management system as described in Section 12.1.

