## SUMMARY

**Rationale:** Out-of-hospital cardiac arrest (OHCA) is a leading cause of global mortality. Delays to initiation of cardiopulmonary resuscitation (CPR) should be as short as possible to achieve the highest survival chance. To reduce treatment delays automated cardiac arrest detection and call for help would be ideal. Photoplethysmography (PPG) is an optical technique often used in sport/smartwatches to monitor heart rhythm at the skin and based on previous studies it seems to have potential to detect circulatory arrest.

**Objective:** To study photoplethysmography signals during 1) induced circulatory arrest; 2) cardiac rhythms without circulatory arrest, and to construct a PPG-based algorithm for circulatory arrest detection.

**Study design:** Prospective multicenter observational study.

**Study population:** 1) Patients scheduled for defibrillation testing after (subcutaneous) implantable cardioverter defibrillator (ICD) implantation; 2) Patients undergoing transcatheter aortic valve replacement (TAVR) with intended rapid ventricular pacing; 3) Patients undergoing ventricular tachycardia ablation.

**Intervention:** Patients will be equipped with a wristband with a PPG-sensor to record PPG signals during hospital stay including during induced circulatory arrests. The circulatory arrest inductions are part of routine practice during above-described procedures and are not a study-related intervention. In case this is not routine practice, an arterial line will be inserted as reference standard for circulatory arrest.

**Main study parameters/endpoints:** Primary endpoints: Sensitivity for circulatory arrest and false positive circulatory arrest alarms.. Secondary endpoints: Positive predictive value for circulatory arrest, Specificity for detection of pulsatile PPG signal, PPG-signal characteristics.

**Nature and extent of the burden and risks associated with participation, benefit and group relatedness:** Given the observational nature of this study and the non-invasive comfortable wristband used for PPG signal recording, the medical risk associated with study participation is negligible. Insertion of an arterial line may carry small risks as outlined in this protocol.

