A previous study in animals has shown feasibility of detection of hemodynamically unstable cardiac arrhythmias using a single derived parameter of the PPG signal (8). Additionally, high correlation was shown between changes in blood pressure and PPG output. In cardiac arrest patients, PPG is under active investigation to detect return of spontaneous circulation (ROSC) during resuscitation and seems to perform even better than manual pulse palpation (9-11). In contrast to the electrocardiogram (ECG) reflecting electrical activity of the heart, PPG provides assessment of hemodynamic status, and therefore functions more as a derivative of the mechanical activity of the heart. This is important as it enables not only detection of ventricular fibrillation and asystole, but also pulseless electrical activity, which is the initial cardiac rhythm in about 20% of cardiac arrests (12).

In the DETECT-project, we aim to further develop an existing medically oriented wristband to fulfil the goal of automated cardiac arrest detection and activation the emergency

medical chain. In the present DETECT-1 study, we will study PPG signals in relation to induced circulatory arrests and develop a PPG-based algorithm for detection of circulatory arrest.

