### 4.4 Sample size calculation

Targeting a desired sensitivity of 95%, 200 true events allow estimation of sensitivity with precision (expressed as expected width of the 95% confidence interval) of +/- 3%, which is considered adequate. As for specificity, a substantially larger number of “non-events” can be sampled, precision for estimating specificity will be larger.

In this study, we will primarily collect data of induced circulatory arrest, obtained during controlled settings with appropriate reference standards (ECG and (invasive) blood pressure measurements). To collect a sufficient amount of PPG data with true events, the

sample size will be 276 patients consisting of an estimated number of n=200 TAVR-patients (event rate 1/1), n=20 ICD-patients (event rate 1/1) and n=56 VT-ablation patients (event rate 1/3). In case ventricular fibrillation induction or rapid ventricular pacing is not performed or does not result in complete circulatory arrest (as determined on (invasive) blood pressure measurements), the number of patients included will be increased to guarantee the anticipated number of true events, with a maximum of 80 additional patients. Data of the patients without induced circulatory arrest will be used as non-cardiac arrest data.

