### **8.3.1 ICD-patients**

As part of routine practice, after subcutaneous implantable cardioverter defibrillator (ICD) implantation or replacement defibrillation testing is performed to test the ability of the implanted device to sense, detect and terminate ventricular fibrillation appropriately. This involves induction of ventricular fibrillation resulting in short-lasting circulatory arrest. During the entire procedure patients will wear the wristband. This enables collection of PPG data in settings with and without circulatory arrest. The presence of circulatory arrest is confirmed by simultaneously recorded invasive blood pressure measurements and ECG recordings. Therefore, in patients in whom this is not standard of care, consent will be asked to insert an arterial line into the radial artery to measure blood pressure during ventricular fibrillation to confirm complete circulatory arrest. ECG and invasive blood pressure measurements will be digitally stored and collected. Available echocardiographic data will be collected. The wristband is removed after the procedure. Activities are described in Table 1.

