**Table 1: Study activities**

TAVR-patients			
Outpatient clinic/hospital admission	Admission/Day of TAVR	TAVR	Day(s) after TAVR
Screening: Check in- and exclusion criteria	Apply wristband for continuous PPG recording	Continue PPG recording using the wristband.	Collect echocardiographic data
Informed consent if eligible		Save invasive (blood) pressure measurements	
Collect baseline data including available echocardiographic data		Annotate rapid ventricular pacing and save ECG monitoring	
		Remove wristband after the procedure	

ICD-patients/VT ablation patients		
Outpatient clinic/hospital admission	Admission	ICD implantation with defibrillation testing
Screening: Check in- and exclusion criteria	Apply wristband for continuous PPG recording	Continue PPG recording using the wristband

Informed consent if eligible	12-lead ECG	Insert an arterial line in the radial artery (opposite arm to the wristband)
Collect baseline data including available echocardiographic data		Initiate and save (non-)invasive blood pressure measurements
		Annotate defibrillation testing and save ECG monitoring
		Remove arterial line and wristband after the procedure

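### The reference standard for arrest in ICD and VT-ablation patients is contradictory, so inductions without an arterial line can enter the second validation as arrest or control without a valid reference

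*Protocol*

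**What the plan says.** Three places in the Protocol make invasive pressure the reference. The Summary says that, where it is not already routine, "an arterial line will be inserted as reference standard for circulatory arrest". Section 8.3.1 (ICD patients) says "The presence of circulatory arrest is confirmed by simultaneously recorded invasive blood pressure measurements and ECG recordings", and 8.3.2 (VT ablation) repeats that sentence. None of the three states an exception.

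Three other places loosen this:

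- Section 13.1: "Only for ICD/VT ablation patients, we will ask additional consent to insert an arterial line in the radial artery", followed by "In case consent is not given, patients can participate without arterial line insertion".
- Section 4.4 describes the reference as "appropriate reference standards (ECG and (invasive) blood pressure measurements", with invasive in brackets. It uses the same brackets where it says how complete arrest is judged.
- Table 1, for ICD and VT-ablation patients: "Initiate and save (non-)invasive blood pressure measurements".

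Two rules then decide where the data go. Section 10 builds the second (external) validation from the final 50 inclusions with at least one induced event, all of them VT-ablation or s-ICD patients, and includes tachycardias as well as VF. It does not mention an arterial line. Section 4.4 assigns patients in whom no arrest was induced to the non-arrest data, and Section 10 checks all non-arrest data for false alarms.

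**The concern.** A patient who declines the line cannot meet the standard in 8.3, yet remains in the study and can be among the 50. The Protocol gives two incompatible signals about what then decides whether an induction was an arrest.

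VT is the most exposed rhythm. A VT may or may not abolish output; the secondary objectives themselves separate hemodynamically stable from unstable arrhythmias. The introduction also explains why ECG cannot settle the matter: "In contrast to the electrocardiogram (ECG) reflecting electrical activity of the heart, PPG provides assessment of hemodynamic status".

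The second validation is the cohort that Section 10 regards as closest to real sudden cardiac arrest, added because TAVR pacing is not physiologic. A wrong label there moves an episode to the other side of the two-by-two table, so both parts of the main endpoint, sensitivity and false positive alarms, are exposed.

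**Working it through.** **1. The plan's own precision figure.** Section 4.4 gives 95% sensitivity, 200 events and ±3%. Half-width = 1.96 × √(0.95 × 0.05 / 200) = 0.0302, so the figure reproduces. It does not depend on the reference-standard question.

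**2. The same formula for the second validation.** Taking one event per inclusion (an assumption), n = 50: 1.96 × √(0.95 × 0.05 / 50) = 0.0604, about ±6.0 points. The Wilson interval is 85.1% to 98.4%.

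**3. How much of this comes from VT ablation.** Section 4.4 plans 20 ICD patients at 1/1 and 56 VT-ablation patients at 1/3. Expected events = 20 + 56/3 = 20 + 18.7 = 38.7, and the VT-ablation share is 18.7/38.7 = 48%. The one-third rate covers VT and VF together, so the share that is VT is not known.

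**4. Where an induction without a line goes.** There are two readings.

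- *Section 4.4 and Table 1 govern.* Non-invasive pressure may support the label, so a VT that kept output could be called an arrest.
- *Section 8.3 governs.* The induction is unconfirmed. Section 10 names only case and control data, and 4.4 sends patients without an induced arrest to the latter. A real arrest could then sit in the control data.

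Neither reading provides a third category for an undetermined episode.

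**5. Effect of one wrong label.** Assume 50 events and a true sensitivity of 95%, so 47.5 expected detections.

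| Wrong label | Algorithm | Effect |
|---|---|---|
| Pulsatile VT called arrest | silent (correct) | counted as a miss: 0.95 × 49/50 = 93.1%, down 1.9 points |
| Pulsatile VT called arrest | alarms (false) | counted as a detection; the false alarm disappears |
| Pulseless VT called control | alarms (correct) | 46.5/49 = 94.9%, down 0.1 point; one false alarm added |
| Pulseless VT called control | silent (a miss) | 47.5/49 = 96.9%, up 1.9 points |

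For the first row, if the algorithm is assumed to alarm on 2% of pulsatile episodes, the cost is (0.95 − 0.02)/50 = 1.86 points, again about 1.9. The table shows that neither the direction nor the size can be fixed in advance.

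**The case against.** The strongest reply is that 8.3 already states the rule for exactly these groups. Section 13.1 only permits participation; it does not say that an induction without a line counts as an event. On that reading such inductions are simply unconfirmed, and labelling of segments is ordinary SAP material. This answers half of the point: it would keep these episodes out of the true events. It does not keep them out of the control data, and a SAP would not remove conflicting statements from the Protocol.

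Several stronger readings are tempting, and the Protocol does not support them.

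- *That 4.4 adopts non-invasive pressure as a reference.* It does so only by implication, through brackets. Its clause on incomplete arrest is a rule for enlarging the sample and names VF induction and rapid pacing, not VT. Table 1 lists data to be saved; it is not a definition of arrest.
- *That a cuff reading would decide.* No non-invasive device or method is named. The inductions are described as short-lasting and no continuous non-invasive method is given, so doubt is reasonable, but it is a methodological judgement.
- *That the bias can be put in a range.* Assuming 10–50% without a line and 25–50% of those VTs with preserved output would give an apparent sensitivity of 93.9% to 83.5% on 38.7 events. None of those shares is in the Protocol, all 18.7 VT-ablation events are treated as VT, and the cohort is defined as 50 inclusions.
- *That ECG alone settles VF.* Section 8.3.1 seeks the line in VF in order to confirm complete arrest, and 4.4 foresees VF induction that falls short of it.
- *That letting patients decline the line is the error.* It is a defensible choice for a study-only invasive procedure with listed complications.

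**Conclusion.** The point holds as a contradiction about the reference standard, with a real consequence for the second validation. The Summary and 8.3 require simultaneous invasive pressure and ECG; 13.1 admits patients in whom this is impossible; 4.4 and Table 1 leave room for non-invasive pressure; and Section 10 neither requires a line nor sets such inductions aside.

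The size is unknown, because the Protocol gives neither the share without a line nor the VT/VF split. What can be said is that, with 50 events, one event per inclusion and 95% true sensitivity, a single wrong label can shift sensitivity by about 1.9 points either way, against a half-width of about 6.0 points. A few wrong labels in the same direction would match the sampling error: three correct silences counted as misses give 0.95 × 47/50 = 89.3%.

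A reader might infer that the main sensitivity estimate is also unsafe. The Protocol does not support that: development and internal validation rest mainly on TAVR patients, in whom 8.3.2 (TAVR patients) says an arterial line is routine. The sensitivity problem is centred on the second validation. The false-alarm count is affected to the extent that unverified ICD or VT-ablation inductions enter the non-arrest data.

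**What to change.** Keep participation without a line, and reconcile the Summary, 4.4, 8.3.1, 8.3.2 (VT ablation), Table 1 and 13.1 so that they state one reference standard and what happens when it is not available. In 4.4 and Section 10:

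1. State that an induced episode counts as a true event in the main second-validation analysis only with simultaneous invasive pressure and ECG.
2. Leave induction segments without invasive pressure out of both the arrest and the control data, and keep the rest of that patient's recording as control.
3. Report ECG-documented VF without a line separately, as a sensitivity analysis.
4. Give the number of arrests by reference type.

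This changes no procedure and no consent. The cost is that somewhat fewer events count in the 50-inclusion cohort. By the formula in step 2 of the working, the half-width would go from 6.0 points at 50 events to 1.96 × √(0.0475/45) = 6.4 points at 45, or 1.96 × √(0.0475/40) = 6.8 points at 40. The 45 and 40 are illustrations, since the number lost is not known.

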### 13.2 Synthesis

Automated cardiac arrest detection may be an important next step in outcome improvement of OHCA-patients given the extreme importance of short treatment delays. Based on animal studies, circulatory arrest detection seems possible using PPG recordings. In this DETECT-1 study in patients, we will collect PPG data of induced circulatory arrests to develop an PPG-based algorithm for circulatory arrest detection, with the overall goal of

the DETECT project to develop a wristband with the functionality to automatically detect cardiac arrest and activate the emergency medical chain.

**Attachments**

Investigational Medical Device Dossier CardioWatch 287-2

Medical Device File CardioWatch 287-2

Certificate of Compliance CardioWatch 287-2

Quality Management System Certificate Corsano Health B.V.

Instruction Manual CardioWatch 287 (only for investigators)

Cloud Data Management Description
